6.6.1. Hemorrhage

Bleeding events have occurred in subjects with relapsed/refractory chronic lymphocytic leukemia (CLL) and relapsed/refractory non-Hodgkin's lymphoma (NHL) who received tirabrutinib as monotherapy. These include minor hemorrhagic events such as contusion, hematoma, and petechiae, and major hemorrhagic events such as small intestinal hemorrhage and subdural hematoma.

Consider interrupting treatment with tirabrutinib for up to 7 days prior to surgery or other interventions associated with a significant risk of bleeding and resuming treatment once hemostasis is achieved.

Subjects should be monitored for signs of bleeding and treated appropriately.

6.6.2. Dermatological and Hypersensitivity Events

Subjects receiving idelalisib and tirabrutinib with \geq Grade 3 rash have generally presented with a maculopapular rash on the trunk and extremities that is occasionally associated with fever and/or pruritus and responded to treatment with diphenhydramine and/or topical or oral corticosteroids.

For subjects who develop a severe rash for which an underlying etiology cannot be identified (e.g., infection, co-suspect drug), study drug should be interrupted. Resumption of study drug should be considered once rash resolves.

Hypersensitivity symptoms can occur after previous exposure and very rarely with the first infusion. If a hypersensitivity reaction is suspected during or after an infusion, the infusion must be stopped and treatment permanently discontinued. Patients with known hypersensitivity to obinutuzumab must not be treated. Subjects receiving obinutuzumab may also experience hypersensitivity reactions with immediate (e.g. anaphylaxis) and delayed onset (e.g. serum sickness); these may be difficult to distinguish from infusion related reactions.

If a hypersensitivity reaction is suspected during or after an obinutuzumab infusion, the infusion must be stopped and treatment permanently discontinued.

If patients experience a hypersensitivity reaction whilst on tirabrutinib, consideration should be given to interruption or discontinuation.

Severe cutaneous reactions, including fatal events of Stevens-Johnson syndrome (SJS), toxic epidermal necrolysis (TEN) and **Drug Reaction with Eosinophilia and Systemic Symptoms (DRESS)**, have been reported in subjects receiving idelalisib and anti-CD20 antibody therapy. If SJS, TEN or DRESS is suspected, all coadministered medications associated with SJS, TEN or DRESS including (if applicable) those for prophylaxis of pneumocystis jirovecii or tumor lysis, should be interrupted and the subject treated accordingly.

6.6.3. Gastrointestinal Events

[figure not shown]
Isolated cases of gastrointestinal inflammation (eg, stomatitis, colitis, cecitis) have been noted in subjects receiving idelalisib or anti-CD20 therapy. Rare cases of gastrointestinal perforation have occurred, generally in the setting of occult carcinoma, mesenteric embolus or diverticular disease. Study treatment should be discontinued in subjects who experience bowel perforation.

Cholangitis manifest as hyperbilirubinemia out of proportion to serum transaminase elevations has been observed. While disease-related factors, neutropenia, toxicity from prior therapies, effects of ongoing supportive care, or pre-existing cholelithiasis may have initiated such events, it is possible that idelalisib played a contributory role. In such subjects, rechallenge with idelalisib has been possible and has not been associated with other severe adverse events. Subjects who have developed evidence of diarrhea or colitis during idelalisib therapy have been successfully treated with antidiarrheals (eg, loperamide) and with enteric steroidal (eg, budesonide) or non-steroidal (eg sulfasalazine [Azulfidine[®]]) anti-inflammatory agents and have been able to continue or resume idelalisib.

For study subjects who develop severe abdominal pain the possibility of a bowel obstruction or perforation should be considered. Appropriate clinical and radiographic examination should be performed and supportive care or surgical intervention should be considered. Upon recovery, rituximab may be resumed.

Among idelalisib-treated patients who reported diarrhea or colitis, the median time to onset of any grade diarrhea or colitis was 1.9 months (range, 0.0 29.8), of grade 1 or 2 was 1.5 months (range, 0.0 15.2) and of grade 3 or 4 was 7.1 months (range, 0.5 29.8). Kaplan Meier curves of time to onset of diarrhea or colitis are shown for all idelalisib- treated patients in [Figure 6-1 {Coutre 2015}](#).

Figure 6-1. Kaplan-Meier Curve of Time to Diarrhea or Colitis

Idelalisib-associated severe diarrhea responds poorly to antimotility agents however, median time to resolution ranged between 1 week and 1 month across trials following interruption of idelalisib treatment and, in some instances, initiation of corticosteroid treatment {Gilead Sciences Inc 2014}.

For subjects who develop persistent diarrhea, causes related to concomitant medications or gastrointestinal infections such as Clostridium difficile (particularly for patients recently treated with broad spectrum antibiotics), Shigella, Campylobacter, Yersinia and CMV should be considered and treated if appropriate. Depending upon the clinical circumstances, endoscopy and biopsy, with bacterial and viral IHC staining should be considered. In the event that an infectious cause is not identified, an antimotility agent (eg, loperamide) may lessen symptoms and intervention with enteric steroidal (eg, budesonide) or non-steroidal (eg, sulfasalazine) anti-inflammatory agents should be considered. In some subjects, rechallenge with idelalisib at a lower dose level has resulted in recurrence of symptoms in some but not all subjects and has not been associated with other severe adverse events.

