3.4. Criteria for Discontinuation of Study Treatment

Study medication may be discontinued in the following instances:

- Documented progression of CLL
- Non-study treatment for CLL
- Development of malignant disease requiring systemic therapy
- Pregnancy
- Investigator discretion
- Non-compliance with study treatment
- Severe protocol violation
- Subject request to discontinue for any reason
- Lost to follow-up
- Death
- Study termination by the sponsor
- Intercurrent illness that would, in the judgment of the investigator, affect assessments of clinical status to a significant degree
- Unacceptable toxicity, as defined in the toxicity management section of the protocol (Section 6.5), or toxicity that, in the judgment of the investigator, compromises the ability to continue study-specific procedures or is considered to not be in the subject's best interest

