4.3. Exclusion Criteria

Subjects who meet any of the following exclusion criteria are not eligible for participation in this study:

- Known transformation of CLL (ie, Richter's transformation, prolymphocytic leukemia)
- Known CNS involvement
- Progression on treatment with any inhibitor of BTK, SYK, PI3K, BCL-2, or obinutuzumab. The treatment and disease response history of subjects with prior treatment with agents in these classes should be reviewed by the sponsor or the GCLLSG study office centrally prior to enrollment to clarify sensitivity to these treatments.
- Any treatment for CLL other than corticosteroids for symptomatic management within 28 days of the start of study treatment
- Participation on a concurrent therapeutic clinical trial unless all treatment is complete with only ongoing surveillance
- Diagnosis of or concern for progressive multifocal leukoencephalopathy
- History of myelodysplastic syndrome or another malignancy other than CLL, *except* for the following: any malignancy that has been in complete remission for 3 years, adequately treated local basal cell or squamous cell carcinoma of the skin, cervical carcinoma in situ, superficial bladder cancer, asymptomatic prostate cancer without known metastatic disease and with no requirement for therapy or requiring only hormonal therapy and with normal prostate-specific antigen for ≥ 1 year prior to start of study therapy
- Active infection requiring systemic therapy
- Pregnant or nursing women (a negative pregnancy test is required for all women of childbearing potential within 7 days before start of treatment and monthly during therapy)
- Active autoimmune disease including autoimmune hemolytic anemia or idiopathic thrombocytopenic purpura requiring a higher corticosteroid equivalent than prednisone 10 mg daily. Higher doses of corticosteroids prescribed for any indication must be stopped >14 days prior to randomization or enrollment; exceptions may be made for corticosteroids prescribed specifically for management of CLL symptoms after discussion with the study medical monitor.

- Diagnosis of inflammatory bowel disease or ongoing symptomatic pneumonitis
- Ongoing CMV infection, treatment or prophylaxis for CMV within the past 28 days

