1.2. Study Design

This is a Phase 2, prospective, open-label, multicenter trial to evaluate the safety and efficacy of the combination of tirabrutinib and idelalisib with and without obinutuzumab in subjects with relapsed or refractory CLL.

Eligible subjects will be randomized in a 1:1 manner to one of the following two arms, stratified by the presence of 17p deletion/TP53 mutation (del17p/TP53mut) in CLL cells:

- Arm A: tirabrutinib + idelalisib
- Arm B: tirabrutinib + idelalisib + obinutuzumab

With Amendment 3, randomization was discontinued. All subsequent subjects will be enrolled into Arm B.

Duration of Treatment:

Tirabrutinib 80 mg and idelalisib 100 mg will be self-administered orally once daily. Dosing of both agents will begin on Week 1 Day 1 of the study and thereafter continue for up to 104 weeks in the absence of disease progression, unacceptable toxicity, or documentation of complete remission (CR) with bone marrow minimal residual disease (MRD) negativity (CR/BM MRD-). If CR/BM MRD- is documented on study, treatment will stop after the earlier of:

- i) an additional 3 months of therapy or
- ii) 104 weeks of total treatment.

Obinutuzumab will be administered as 8 intravenous infusions of 1000 mg each over 21 weeks. A test dose of 100 mg will be administered on Week 1 Day 1. If this dose is tolerated, the remainder of the full dose may be subsequently administered on Day 1. Alternatively, the remaining 900 mg will be administered on Day 2. Subsequent infusions will be administered on Week 2 Day 1, Week 3 Day 1, Week 5 Day 1 and then every 4 weeks through Week 21.

This study will continue to monitor subjects for up to 30 days post end of treatment, or up to Week 25 should a subject discontinue treatment prior to Week 25 for reasons other than disease progression.

Efficacy Assessment Schedule:

Tumor response assessment per modified International Workshop on CLL (IWCLL) 2008 criteria will be performed at the Week 25 visit, with evaluation of areas affected by CLL during the screening evaluation. During the treatment phase, additional response assessment per IWCLL 2008 criteria may be performed as clinically indicated.

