6.1. Primary Efficacy Endpoint

6.1.1. Definition of the Primary Efficacy Endpoint

The primary efficacy endpoint of this study is the rate of CR per modified IWCLL 2008 criteria {Hallek 2008} at Week 25, which is defined as the proportion of subjects who achieved CR/CRi at Week 25. Subjects who received anti-cancer therapy other than the study drug prior to achieving CR/CRi at Week 25, will be considered as nonresponders for CR/CRi and will be included in the denominator when calculating the CR rate at Week 25.

The analysis window of Week 25 response assessment is defined as $24 \times 7 \pm 28$ days (inclusive) starting from first dose. This analysis window is extended from the visit window to capture the assessments outside the scheduled window. If there are multiple assessments within the analysis window, records will be chosen based on rules specified in Section 3.8.3.

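### Protocol 6.6.3 names rituximab, which is in neither arm, as the drug to resume after a suspected bowel obstruction or perforation, and the surrounding rules for perforation disagree with each other

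*Protocol*

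**What the plan says.** Protocol 6.6.3 (Gastrointestinal Events) has two places that bear on a serious bowel event. The first paragraph, on gastrointestinal inflammation and perforation, says: "Study treatment should be discontinued in subjects who experience bowel perforation". A later paragraph deals with severe abdominal pain. It asks the investigator to consider obstruction or perforation, to examine and image the subject, and to consider supportive care or surgery. It then ends: "Upon recovery, rituximab may be resumed".

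The SAP, Section 1.2, gives the arms as "Arm A: tirabrutinib + idelalisib" and "Arm B: tirabrutinib + idelalisib + obinutuzumab". Protocol 4.3 excludes subjects who have had "Any treatment for CLL other than corticosteroids for symptomatic management within 28 days of the start of study treatment".

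Dose rules for the same events also stand in the following places:

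- Protocol 6.5, in the text before Table 6-2, treats the tables as guidelines. It lists bowel perforation among the exceptions for which idelalisib must be stopped.
- Table 6-2 has a bowel perforation row that applies to any grade.
- Table 6-3 covers obinutuzumab.
- Protocol 5.3.2 allows obinutuzumab to be delayed for related adverse events or intercurrent illness.

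**The concern.** Section 6.6.3 is working guidance for a potentially life-threatening event, not background. A site that reaches the end of the abdominal-pain paragraph wants to know which of the subject's drugs may restart, and when. The sentence names a drug that the subject does not have and says nothing about the two or three that the subject does have.

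If the site then looks elsewhere, the answer depends on which page it opens. Sites could handle the same event differently, and each could point to protocol text in support. What is at stake is the safety of the affected subject and consistent conduct across about 25 centres.

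**Working it through.** No arithmetic applies, because the point rests on no sample size, rate or event count. The check is a comparison of texts.

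**Step 1: is rituximab a study drug?** No. Arm A contains no anti-CD20 antibody, and the antibody in Arm B is obinutuzumab. Elsewhere in the protocol rituximab appears only in background on other studies and approvals, as an example in the section on progressive multifocal leukoencephalopathy (6.6.11), and in the references.

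**Step 2: could a subject already be on it?** An eligible subject should not be. CLL treatment other than corticosteroids for symptoms is excluded in the 28 days before study treatment starts. There is nothing to resume, so the sentence cannot be followed as written.

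**Step 3: what do the other rules say after perforation?**

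| Place | Tirabrutinib | Idelalisib | Obinutuzumab |
|---|---|---|---|
| 6.6.3, first paragraph | Stop (part of study treatment) | Stop | Stop |
| 6.6.3, abdominal-pain paragraph | Not mentioned | Not mentioned | Not mentioned; restart on recovery allowed if the drug name is read as obinutuzumab |
| 6.5, text before Table 6-2 | No rule | Must stop | No rule |
| Table 6-2, perforation row, any grade | Keep dose and schedule | Stop | Not covered |
| Table 6-3 | Not covered | Not covered | No perforation or obstruction row. General row for Grade 3 or higher, if judged related: delay, then full dose or stop at the investigator's discretion |
| 5.3.2 | Not covered | Not covered | Delay allowed for related events or intercurrent illness |

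Reading down the columns:

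- **Idelalisib:** every place that gives a rule after perforation agrees.
- **Tirabrutinib:** 6.6.3 stops it and Table 6-2 keeps it unchanged. This is a direct contradiction.
- **Obinutuzumab:** 6.6.3 stops it as part of study treatment, while the general row of Table 6-3 allows a return to full dose. Table 6-3 does have rows for gastrointestinal inflammation and diarrhoea, but they mention neither perforation nor obstruction.

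**Step 4: what do they say after obstruction without perforation?** The discontinuation sentence in 6.6.3 does not reach this case. The oral drugs fall under the graded rows for other non-haematological events in Table 6-2, and obinutuzumab under the matching rows of Table 6-3 and the delay provision. The only restart sentence written for this situation is the rituximab one.

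**Step 5: does replacing the drug name solve it?** Not on its own. Suppose the sentence read obinutuzumab. The paragraph covers possible perforation and allows resumption on recovery without excluding subjects in whom perforation was confirmed, while the first paragraph stops study treatment in those subjects.

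**The case against.** The strongest reply is that this is a wrong drug name in one permissive sentence, probably carried over from another protocol (an inference), and that no investigator would act on it. The rest can also be read together. The first paragraph is the specific rule for confirmed perforation, and the later paragraph is general guidance for pain in which perforation is only suspected. On that reading the two paragraphs of 6.6.3 do not contradict each other. Much of this stands. The two paragraphs are ambiguous rather than irreconcilable, and actual use of rituximab is unlikely. The reply does not, however, remove the conflict between 6.6.3 and Table 6-2 on tirabrutinib, and it does not supply the missing restart rule.

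A reader might infer four stronger things. The documents support none of them.

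- **That the sentence authorises a non-study antibody.** It speaks of resuming, and no subject should have rituximab to resume.
- **That following it produces a nonresponder.** The SAP rule in 6.1.1 reads "Subjects who received anti-cancer therapy other than the study drug prior to achieving CR/CRi at Week 25, will be considered as nonresponders", so it applies only when the other therapy comes before the response, and it requires that the antibody actually be given. Protocol 3.4 does list "Non-study treatment for CLL", but under the permissive lead-in "Study medication may be discontinued in the following instances".
- **That it would remove the difference between the arms.** SAP 3.1 and 3.3 state that the treatments are not to be compared, and enrolment to Arm A ended with Amendment 3.
- **That obinutuzumab is left with no usable rule.** The study-treatment sentence in 6.6.3, the delay provision in 5.3.2 and the general row of Table 6-3 all apply to it. What is missing is a single consistent rule.

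**Conclusion.** The point holds as an internal inconsistency in safety guidance. The only restart instruction in the abdominal-pain paragraph names a drug outside the trial. After perforation the instructions for tirabrutinib contradict each other, and those for obinutuzumab come from general provisions that do not agree.

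The size is textual: one sentence, one direct contradiction and one drug without a consistent rule. The documents give no rate for obstruction or perforation in this population, and the protocol describes perforation as rare, so no effect on the complete remission rate should be claimed.

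The conclusion rests on two readings: that *study treatment* in 6.6.3 means all the drugs of the subject's arm, and that the abdominal-pain paragraph includes subjects whose perforation is later confirmed. If the second reading is rejected, the wrong drug name and the tirabrutinib conflict remain. The correction should be made because the event is serious and the change is small.

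**What to change.** Remove or correct the rituximab sentence in Protocol 6.6.3. Reconcile that section with the text of 6.5, the perforation row of Table 6-2 and the obinutuzumab rules in Table 6-3 and 5.3.2. The result should state the position of tirabrutinib, idelalisib and obinutuzumab separately for two situations: confirmed perforation, and obstruction without perforation. Which rule applies to each drug is for the sponsor's clinical team; this review proposes none.

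The cost is a short protocol correction, submission to the ethics committee with documented approval as Protocol 9.2.1 requires, and a letter to sites. No new data, procedures or analyses are needed, and the SAP does not change.

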The safety and efficacy of obinutuzumab combined with idelalisib 150 mg twice daily was evaluated in a randomized, open-label Phase 3 study (GS-US-312-0118); this study was subsequently terminated due to safety concerns regarding the use of idelalisib at the dose of 150 mg twice daily in first-line treatment of CLL. A total of 57 subjects with previously untreated CLL were enrolled in Study GS-US-312-0118 at the time of study termination; of these, 33 were randomized to the combination of idelalisib with obinutuzumab and 32 were treated with this combination. Of the 32 subjects treated with the combination, the median duration of exposure was 9 weeks (range: 0.7 – 45 weeks). Treatment-emergent AEs reported

in >15% of these subjects were as follows (any grade/ \geq Grade 3): ALT increased (38%/31%); AST increased (38%/25%); neutropenia (31%/28%); anemia (25%/13%); diarrhea (25%/6%); and infusion-related reaction (19%/9%). A total of 14 subjects reported a treatment-emergent serious adverse event (SAE), of which the majority were due to infection (16%) [pneumonia (3%), sepsis (3%), bronchitis (3%), lung infection (3%), upper respiratory tract infection (3%)]; the remainder were due to anemia (6%), pneumonitis (6%), febrile neutropenia (3%), diarrhea (3%), enteritis (3%), pyrexia (3%), and chills (3%). A total of 3 subjects discontinued treatment with idelalisib due to an AE: 1 each for colitis (Grade 3), sepsis (Grade 3), and liver function test abnormality (Grade 4); 1 subject discontinued obinutuzumab due to sepsis (Grade 3). No deaths occurred on the study.

Obinutuzumab (Gazyva[®]/Gazyvaro[®]) is approved in the US and EU for use in combination with chlorambucil for the treatment of patients with previously untreated CLL.

For further information on obinutuzumab, refer to the local prescribing information (PI).

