Based on data from the clinical development programs and post-marketing pharmacovigilance for idelalisib and other PI3K inhibitors {[Flinn 2013](#)} alone or in combination with chemotherapy or anti-CD20 antibodies, AEs including infection, diarrhea/colitis, transaminase elevation, rash, neutropenia, organizing pneumonia, and pneumonitis may be observed in subjects treated with idelalisib. Guidelines for managing these AEs have been incorporated into this protocol. The monitoring to be performed and the actions to be taken in response to toxicity are based on experience with interruption, dose modification, rechallenge, and re-escalation with idelalisib treatment.

A recent aggregate analysis of three Phase 3 trials in front-line CLL (1) and early-line relapsed iNHL (2) demonstrated an increase in SAEs and deaths, primarily due to infections, with the addition of idelalisib to standard therapy, particularly in the first 6 months of therapy. The risk of death was higher in bendamustine containing regimens. In light of this additional idelalisib safety data, pneumocystis prophylaxis, CMV surveillance, and increased monitoring for neutropenia in the first 6 months have been instituted in conjunction with idelalisib therapy, including in this study protocol.

In contrast to the studies in which increased deaths from infection in idelalisib treated patients were noted, this study is limited to subjects with previously-treated CLL there is a clear benefit of idelalisib treatment in this population. Two large Phase 3 clinical trials {[Furman 2014](#), [Zelenetz 2015](#)} have shown improved PFS and OS for previously-treated CLL patients with the addition of idelalisib to either the combination of bendamustine and rituximab or rituximab alone. Furthermore, the decreased dose of idelalisib 100 mg once daily used in the combination setting, including in this study, is predicted to reduce idelalisib exposure (AUC and C_{min}) by ~50% and has the potential to reduce idelalisib-associated toxicities while maintaining efficacy when administered in combination.

Please refer to the IB for more information. Obinutuzumab

Obinutuzumab (Gazyva[®]/Gazyvaro[®]) is an anti-CD20 mAb which is approved in the US and EU for use in combination with chlorambucil for the treatment of patients with previously untreated CLL. The safety reference documents for obinutuzumab will be the Summary of Product Characteristics (SmPC). Please refer to the SmPC for further information.

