6.2.10.1. Evaluation for Gastrointestinal Events/Colitis

For subjects who report diarrhea or colitis, obtain history of onset and duration, including description of the number of stools and stool composition (watery, bloody, nocturnal), travel history, diet changes and medication review to identify possible causes. Perform physical examination, including assessment for fever, dizziness, abdominal pain/cramping, and weakness (ie, evaluate for sepsis, bowel obstruction, dehydration). If unclear, consider upper and lower tract endoscopy with biopsy. Laboratory evaluation for infectious causes of diarrhea should be performed and in the absence of a diagnosis, endoscopy should be considered with evaluation for CMV and other infectious pathology.

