Grade 4	Discontinue tirabrutinib and idelalisib.	

a) CMV should be diagnosed using clinical or laboratory criteria per established institutional standard

Table 6-3. Dose Adjustment Guidelines for Subjects Receiving Obinutuzumab

NCI CTCAE Grade	Recommendation
	Toxicity attributable to obinutuzumab
HEMATOLOGICAL ADVERSE EVENTS*	
Neutropenia^a	
Grade ≤ 2 neutropenia	Maintain current dose level and schedule.
Grade 3 neutropenia	Maintain current dose level and schedule. Consider G-CSF support.
Grade 4 neutropenia (or occurrence of neutropenic fever or infection)	Delay obinutuzumab until Grade ≤ 2 (ANC ≥ 1 × 10 ⁹ /L) and/or neutropenic fever or infection is resolved; thereafter, resume at full dose. Consider G-CSF support to avoid delays. If delay is > 4 weeks, discontinue obinutuzumab.
Thrombocytopenia	
Grade ≤3	Maintain current dose level and schedule.
Grade 4	Delay obinutuzumab until Grade ≤ 3 (platelets ≥ 25 × 10 ⁹ /L); thereafter, resume at full dose. If delay is > 4 weeks, discontinue obinutuzumab, unless the Grade 4 thrombocytopenia occurred after the first 3 weekly doses.
Hemorrhage	
N/A	
Hold obinutuzumab in case of platelets < 20,000/μL. If Day 8 is delayed then skip Day 8 and administer Day 15 as previously scheduled (if symptomatic bleeding has resolved). If Day 15 is delayed then skip Day 15 dosing and administer Day 29 of obinutuzumab as scheduled.
 
At the discretion of the study investigator, for subjects who are on low molecular weight heparin (LMWH), when thrombocytopenia with platelets <20,000/μL develops, reduce the dose of LMWH or new oral anticoagulants (NOAC) used.
 
Hold tirabrutinib and obinutuzumab for clinically significant bleeding (irrespective of platelet count) until it resolves.

NON-HEMATOLOGICAL ADVERSE EVENTS	
Cutaneous	
Grade ≤2	Maintain current dose level and schedule.
Grade 3 or 4	Delay obinutuzumab until Grade ≤ 1; thereafter, may resume at full dose or discontinue obinutuzumab at investigator discretion.
Gastrointestinal Inflammation/Diarrhea	
Grade ≤1	Maintain current dose level and schedule.
Grade 2	Maintain current dose level and schedule.
Grade 3	Hold idelalisib and obinutuzumab until subject is sufficiently stable to receive further treatment; thereafter maintain full dose and schedule. If recurrent with rechallenge, consider treatment with tirabrutinib alone.

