7.1.7. Adverse Events of Interest

The treatment-emergent AEs of interest (AEI) include:

AEI	Grouped Terms
Hemorrhage/Bleeding	MST-CT Bleeding/Haemorrhage (Appendix 4)
Infections	SOC: Infections and infestations
Hypersensitivity	MST-CT Hypersensitivity (Appendix 5)
Cytopenia	MST: Anemia-related events, leukopenias, neutropenia, thrombocytopenias (Appendix 6)
Cardiac Arrhythmias	MST-CT Cardiac arrhythmia and bradycardia_narrow (Appendix 7)
Diarrhoea	PT: Diarrhoea
Rash	MST-CT Rash - specific to ONC (Appendix 8)

The following summaries will be provided for AEs by SOC, PT, and maximum severity:

- A) TEAE
- B) TEAEs leading to dose modifications or temporary interruption of study drug
- C) TEAEs leading to discontinuation of study drug

A data listing of AEs will be provided by alphabetic ascending order of AE name, then by subject ID.

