Cerebral haemorrhage foetal	10050157
Cerebral haemorrhage neonatal	10008112
Cerebral microhaemorrhage	10067277
Cervix haematoma uterine	10050020
Cervix haemorrhage uterine	10050022
Chest wall haematoma	10076597
Choroidal haematoma	10068642
Choroidal haemorrhage	10008786
Chronic gastrointestinal bleeding	10050399
Chronic pigmented purpura	10072726
Ciliary body haemorrhage	10057417
Circulating anticoagulant	10053627
Clot retraction abnormal	10009669
Clot retraction time prolonged	10009675
Coagulation disorder neonatal	10009732
Coagulation factor decreased	10009736
Coagulation factor deficiency	10067787
Coagulation factor IX level abnormal	10061770
Coagulation factor IX level decreased	10009746
Coagulation factor mutation	10065442
Coagulation factor V level abnormal	10061771
Coagulation factor V level decreased	10009754
Coagulation factor VII level abnormal	10061772
Coagulation factor VII level decreased	10009761
Coagulation factor VIII level abnormal	10061773
Coagulation factor VIII level decreased	10009768
Coagulation factor X level abnormal	10061774
Coagulation factor X level decreased	10009775
Coagulation factor XI level abnormal	10061775
Coagulation factor XI level decreased	10009779
Coagulation factor XII level abnormal	10061776
Coagulation factor XII level decreased	10009783
Coagulation factor XIII level abnormal	10061777
Coagulation factor XIII level decreased	10009787
Coagulation time abnormal	10009791

MEDDRA Preferred Term	PT Code
Coagulation time prolonged	10009799
Coagulopathy	10009802
Coital bleeding	10065019
Colonic haematoma	10009996
Congenital coagulopathy	10063563
Congenital dysfibrinogenaemia	10051123
Conjunctival haemorrhage	10010719
Contusion	10050584
Corneal bleeding	10051558
Cullen's sign	10059029
Cystitis haemorrhagic	10011793
Deep dissecting haematoma	10074718
Diarrhoea haemorrhagic	10012741
Dilutional coagulopathy	10060906
Disseminated intravascular coagulation	10013442
Diverticulitis intestinal haemorrhagic	10013541
Diverticulum intestinal haemorrhagic	10013560
Duodenal ulcer haemorrhage	10013839
Duodenitis haemorrhagic	10013865
Dysfunctional uterine bleeding	10013908
Ear haemorrhage	10014009
Ecchymosis	10014080
Encephalitis haemorrhagic	10014589
Endometriosis	10014778
Enterocolitis haemorrhagic	10014896
Epidural haemorrhage	10073681
Epistaxis	10015090
Ethanol gelation test positive	10062650
Exsanguination	10015719
Extra-axial haemorrhage	10078254
Extradural haematoma	10015769
Extravasation blood	10015867
Eye contusion	10073354

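### The Diarrhoea adverse event of interest in SAP 7.1.7 is a single preferred term, so no planned table counts the subjects with diarrhoea or colitis, the pair that the protocol treats as an idelalisib toxicity

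*Protocol*

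**What the plan says.** SAP 7.1.7 lists seven treatment-emergent adverse events of interest (AEIs). Five are defined by multi-term search lists, for example "MST-CT Rash - specific to ONC", and Infections takes a whole system organ class (SOC). Diarrhoea alone rests on one preferred term (PT). Three summaries by SOC, PT and maximum severity follow for the AEIs: all TEAEs, TEAEs leading to dose modification or temporary interruption, and "TEAEs leading to discontinuation of study drug".

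The protocol usually speaks of diarrhea and colitis together:

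- Section 1.6, on idelalisib risk: "AEs including infection, diarrhea/colitis, transaminase elevation, rash, neutropenia, organizing pneumonia, and pneumonitis may be observed in subjects treated with idelalisib".
- Section 6.2.10.1, one work-up for both: "For subjects who report diarrhea or colitis, obtain history of onset and duration".
- Section 6.6.3, onset data for both: "Among idelalisib-treated patients who reported diarrhea or colitis, the median time to onset of any grade diarrhea or colitis was 1.9 months".
- Table 6-3, for obinutuzumab, one block of rows headed "Gastrointestinal Inflammation/Diarrhea".

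Table 6-2, which covers idelalisib and tirabrutinib, is the exception: its block is headed Diarrhea alone. Its Grade 3 or 4 entry nevertheless points to Section 6.2.10.1, whose title names colitis.

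**The concern.** An event coded as colitis, enterocolitis or enteritis does not meet the AEI definition, so it enters none of the three AEI summaries. Some related terms count under other AEIs. "Diarrhoea haemorrhagic", the haemorrhagic form of enterocolitis and acute haemorrhagic ulcerative colitis are in the bleeding list (Appendix 4), allergic colitis is in the hypersensitivity list (Appendix 5), and neutropenic colitis is in the cytopenia list (Appendix 6). Plain colitis is in no list.

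Safety and tolerability is the secondary objective, and the AEI tables are where a reader would look for a toxicity that the protocol names in advance. As planned, that reader finds simple diarrhoea but not the combined event that protocol 1.6 and 6.6.3 describe.

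**Working it through.** The plan states no figure to reproduce. The check is a comparison of definitions, followed by a small illustration.

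**1. What each planned output holds for an event coded as colitis**

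| Output | Colitis shown? | Subjects with diarrhoea or colitis shown? |
|---|---|---|
| SAP 7.1.7, Diarrhoea AEI (three summaries) | No | No |
| SAP 7.1.6.1, tables by SOC and PT (TEAEs, Grade 3 or higher, SAEs; discontinuation, modification and interruption for each drug) | Yes, on its own PT line | No |
| SAP 7.1.6.1, by-subject listings | Yes | Only by hand count |

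**2. Why rows cannot be added.** SAP 7.1.6.1 counts a subject once per summary line. Let D be the number of subjects with diarrhoea, C the number with colitis and B the number with both. Subjects with either = D + C − B, and no table reports B. The gastrointestinal SOC total does not supply the count either, because it also takes in events such as constipation (26%) and nausea (22%), the rates in the Phase 1b doublet study in protocol 1.3.4.

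**3. Illustration from protocol 1.4.** Of 32 subjects treated with idelalisib plus obinutuzumab, 3 stopped idelalisib for an adverse event: "1 each for colitis (Grade 3), sepsis (Grade 3), and liver function test abnormality (Grade 4"). None of the three stopped for diarrhea. With exact two-sided 90% Clopper-Pearson limits:

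- Diarrhoea term only: 0/32 = 0%. Upper limit = 1 − 0.05^(1/32) = 8.9%.
- Diarrhoea or colitis: 1/32 = 3.1%. Lower limit = 1 − 0.95^(1/32) = 0.2%. Upper limit = 0.95 quantile of Beta(2, 31) = 14.0%.

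The same study shows step 2 at work. Diarrhea of any grade was 25%, and 8/32 is the only count that rounds to it. Adding only the one known colitis case, subjects with either event number 8 + 1 − B. That is 8 (25.0%) if the colitis subject also had diarrhea recorded and 9 (28.1%) if not. The reported percentages do not say which.

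**4. Could it arise here?** The documents give no colitis rate for this regimen, so I assume a range. The chance of at least one case among the 30 planned Arm B subjects is 1 − (1 − q)^30:

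| Assumed colitis rate q | Chance of at least one case in 30 |
|---|---|
| 1% | 26% |
| 3.1% (1/32, the discontinuation share in step 3) | 61% |
| 5% | 79% |
| 10% | 96% |

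Each such subject is 1/30 = 3.3 percentage points of Arm B.

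**The case against.** The strongest reply is that nothing is hidden. SAP 7.1.6.1 tabulates every PT by SOC and maximum severity, including discontinuation, modification and interruption of each drug, and it lists all adverse events by subject. The row labelled Diarrhoea counts Diarrhoea. Protocol 8.6.2 asks for SOC and PT summaries and for no AEI groups, so the protocol's safety endpoint is met without SAP 7.1.7. With about 36 subjects, anyone can count the combined event from the listings. All of this stands, and it limits the point to a gap in presentation.

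It does not remove the gap. The combined count is not prespecified, and a hand count from listings leaves the choice of terms until the data are known. The per-drug tables also do not replace the AEI summaries, which are specified for study drug as a whole.

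A reader might infer more than the documents support:

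- *That colitis disappears from the gastrointestinal reporting.* It stays in the general tables and listings.
- *That the row is biased downward.* It is a descriptive count of the term it names.
- *That colitis is the form most likely to end treatment.* This would rest on one Grade 3 case in another study, in previously untreated CLL at idelalisib 150 mg twice daily. Protocol 6.6.3 says that some subjects with diarrhea or colitis were able to continue or resume idelalisib.
- *That serious gastrointestinal events are missed.* SAP 7.1.7 has no summary of serious events. SAP 7.1.6.1 has one, and it would show diarrhea and enteritis alike.
- *That the protocol always treats the two as one event.* Table 6-2 heads its block Diarrhea alone, and protocol 1.4 reports diarrhea, enteritis and colitis separately.

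**Conclusion.** The point holds as a cheap improvement to SAP 7.1.7. The AEI is narrower than the toxicity the protocol names, and no planned table gives the number of subjects with diarrhoea or colitis. No event is lost, and no efficacy result or general safety table changes.

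The size in this trial cannot be computed. The contrast of 0/32 with 1/32 shows the mechanism in a different dose and population and does not predict this trial; the general discontinuation table would show that case in any event. The conclusion assumes that sites will report some events as colitis, enterocolitis or enteritis and that these will be coded to their own terms. The separate entries in the SAP appendices and the separate reporting in protocol 1.4 make that reasonable.

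**What to change.** Before database finalization, replace the single term in SAP 7.1.7 with a grouped AEI named Diarrhoea/colitis, defined by a closed list of preferred terms in an appendix. The list could hold Diarrhoea, Diarrhoea haemorrhagic, Colitis, Enterocolitis, Enterocolitis haemorrhagic and Enteritis, plus any other colitis terms that the sponsor names there. Count each subject once in the group row of all three AEI summaries, and keep Diarrhoea as its own PT line beneath it.

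The cost is one term list and a rerun of tables already planned. No new data are needed. The SAP already intends to update its search lists to the MedDRA version in use at database finalization, and it says that later changes are documented in the CSR.

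There are two small downsides. The group row is broader than simple diarrhoea, which the retained PT line answers. A few terms will also count under the bleeding, hypersensitivity or cytopenia AEIs, so a footnote should say that the AEI groups overlap and must not be added together.
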